We are not aware of previous assessments of long-term pain outcomes in unselected Danish patients operated with KA. The most widely used numbers originates from a systematic review published in 2012 that used data collected in various countries between 1995-2006.² An updated investigation is important for several reasons. First, surgical techniques and equipment have evolved over the years. Second, introduction of standard treatment with high-dose glucocorticoids should, in theory, have reduced central sensitisation, which is a key aspect of persistent postsurgical pain.^{7,8} Third, implementation of early mobilisation and other enhanced recovery after surgery (ERAS) elements have reduced the mean length of hospital stay from around 10 days in 2000 to a single day in 2021.⁴

For these reasons, we aim to investigate the satisfaction and incidence of persistent pain after KA for osteoarthritis.

Methods

The study is registered at the capital region of Denmark's regional research listing (Pactius) with identifier P-2023-4, approved 4 January 2023. This protocol is registered at ClinicalTrials.gov and is **currently under review**. The resulting paper will be reported according to the CROSS checklist for standardised reporting of survey studies.⁹ Wherever needed, a trained linguist translated questions from English to Danish and vice versa. The Danish and an English version of the questionnaire will be available in the final publication.

Study design: This study is a nationwide cross-sectional survey.

Patient involvement: A panel of KA patients helped develop the questionnaire, i.e., testing and selecting the questions.

Questionnaire: The questionnaire is composed of 22 questions, however patients answering "No" to question 3 skips questions 4-17 concerning pain in the operated knee. Only questions 3, 4, 20, and 21 are mandatory because we wanted to avoid non-respondents. The contact letter in Danish (S1) and full questionnaire in Danish (S2) and English (S3) can be found in the supplementary material. Contact information for the first author (JL) is supplied in the contact letter and the header of the questionnaire, in case the patients have difficulties with filling in the questionnaire, believe they have been contacted mistakenly etc. We used similar or identical questions to those in a survey conducted in 2004 to increase our ability to compare results (i.e., questions 3-5, 8, 10 and 18).¹⁰

The 1st question assesses overall satisfaction with surgery and have been translated directly from the questionnaire used by the Swedish Arthroplasty Register to enable direct comparison.³

Question 2 assesses willingness to repeat surgery, as described by Chestworth et al..¹¹

Question 3 assesses pain frequency with the same response options as the 2004 survey.¹⁰ This question is mandatory due to branching purposes, i.e. respondents without pain can skip questions 4-17.

Question 4 is the 11-point numerical rating scale (NRS) for knee pain, which is widely used and recommended.^{12,13} To facilitate comparison with other studies, we assessed average pain in the last week.¹² This question is also mandatory because it is our primary outcome.

Question 5-9 is the pain dimension of the likert-scale version 3.1 Western Ontario and McMaster Universities Osteoarthritis Index (WOMAC).¹⁴ The instrument is validated for osteoarthritis patients and specifically recommended by the International Association for the Study of Pain (IMMPACT).¹³

Question 10 assesses pain interference on everyday activities. Pain interference is often included in core outcome sets for clinical trials^{13,15} and it is recommended to use disease-specific interference.¹³

Question 11-17 are the Douleur Neuropathique 4 questions (DN4) interview, which can be used to estimate the number of patients with ‘possible’ neuropathic pain.^{16,17} We chose to the DN4 interview over other neuropathic pain measures because it is widely used and validated, short, and available in Danish (from www.mapi-trust.org).¹⁶

Question 18 assesses other chronic pain conditions with an open text field, which we will later categorise. We believe this is more accurate than allowing patients to categorise their pain condition from a predefined list of options.

Question 19 assesses patient-reported use of analgesics, including if the analgesics are taken for pain in the operated knee or not. Again, the type of analgesics is typed into an open text field, as to not restrict respondents to specific medications and to enable responses with typos.

Questions 20 and 21 are on the patient’s current height and weight, recently found to be valid in a Danish E-survey setting.¹⁸

Finally, in question 22 we ask for permission to contact respondents again later.

Sample characteristics: Eligible patients are all adult (18 years or older) patients operated with primary total or medial unicompartmental KA for osteoarthritis between August 1 and November 30, 2023. Legally incompetent citizens, i.e., persons with a legal guardian, will not be asked to participate.

For total KA, we will identify patients from the Danish National Patient Register through the Danish Health Data Authority (SKS-code DM17 [knee osteoarthritis] + KNGB20, KNGB30 or KNGB40 [primary total knee arthroplasty]).

For medial unicompartmental KA, we will identify patients from the Danish National Patient Register through the Danish Health Data Authority (SKS-code DM17 [knee osteoarthritis] + KNGB01 or KNGB11 [primary medial unicompartmental knee arthroplasty]).

The sample size calculation is based on the primary outcome in total KA patients. With an estimated 16% incidence of the primary outcome³ and a 70% response rate,¹⁹ 3172 patients are needed to yield a 95% confidence interval of 3 percentage points (14.6-17.6). In our opinion, this level of certainty is appropriate because differences less than this, may be hard to interpret by clinicians and patients. Sampling patients that were operated during 4 months outside holiday season should yield approximately this number of identified patients.⁴

Baseline data of respondents and non-respondents are gathered from the Danish Knee Arthroplasty Register. To evaluate the generalisability of the study, we will report the respondents’ baseline data and compare them to the non-respondents in Table 1.

Survey administration: In an encrypted fashion, the survey will be sent via ‘Digital Post’ which is linked to the unique Civil Registration (CPR) number using the Research Electronic Data Capture (REDCap) software (www.project-redcap.org). A reminder will be sent to non-respondents 14 days after the first letter. Remaining non-respondents are sent a text-message if their telephone number is registered in the electronic patient file.

For questions with an open text field option, two authors (JL, SS) will independently categorise the responses to minimise errors.

Study preparation: We will not advertise the survey and respondents are not rewarded for participation.

Ethical considerations: The local institutional review board approved the study, and the Danish Health Data Authority will provide contact information for potential respondents. Telephone numbers for non-respondents are found by searching the CPR number in the electronic patient files, but without accessing the patients’ health data. According to Danish legislation, approval from the national ethics committee is neither required nor possible to obtain for survey studies (see attached ‘exempt from notification’ letter from the Danish national ethics committee, S5).

Because we will link survey responses with perioperative data from the Danish Knee Arthroplasty Register, responses are not anonymous. However, only the authors will have access to confidential information and data will be anonymised as soon as possible. Until then, the data are stored pseudonymised at a logged and encrypted drive.

Statistical analyses: The main outcome is the number of patients with moderate or severe persistent postsurgical pain in the operated knee, defined as patients with a numerical rating scale (NRS) score higher than 3.²⁰ We dichotomised the NRS score for our primary outcome because we believe this is more intuitively understood by patients and clinicians. The main outcome will be reported as percentage of all patients with 95% confidence interval, calculated with assumed binomial distribution:

$$p \pm 1.96 \sqrt{\frac{p(1-p)}{n}}$$

Categorical variables, including the individual questions of WOMAC pain domain and DN4 interview, will be reported directly as number of patients (percentage of all patients). The raw NRS score, height and weight are continuous variables and will be reported as median (interquartile range [IQR]) number of respondents.

The five questions in the WOMAC pain domain can be scored 0-4, where 0 is ‘none’ and 4 is ‘extreme’. This results in an overall score of 0-20, which will be reported as median (IQR).

Each of the seven questions in the DN4 interview can be scored 0/1 (no/yes), which results in an overall score of 0-7. A score ≥ 3 constitutes 'possible' neuropathic pain.^{16,17} Both the median (IQR) DN4 interview score and number of patients (percentage of all patients) with possible neuropathic pain will be reported.

We do expect some missing data because incomplete questionnaires may be submitted. Generally, responses will not be imputed. However, we will impute values to calculate summary scores of the WOMAC pain domain and DN4 interview as the median of the reported values within the instrument.

We do not plan to adjust for non-representativeness, but as previously mentioned, baseline characteristics (age, sex, and ASA score) and surgical details (type of anaesthesia, operation length, use of local infiltration analgesia (LIA), use of cement, and surgical complications) of respondents and non-respondents are presented in Table 1.

Data is handled in the most recent version of R (www.r-project.org).²¹

Knowledge dissemination

The survey will be fully reported in an international peer-reviewed journal. In addition, the responses from this survey will be pooled with responses from a similar survey on hip pain. The combined data will be used in two additional studies: 1) to validate the use of prescription registries on analgesic for identifying patients with persistent postsurgical pain,²² and 2) to investigate associations between weight and weight-change and the different outcomes. Both will be published in peer-reviewed journals.

We seek to make the papers freely available (e.g., as preprint at www.medrxiv.org or through open-access publication) and to store the full dataset at the Danish national archive (www.rigsarkivet.dk). Moreover, the results will be presented at meetings and conferences, predominantly for orthopaedic surgeons, anaesthetists, pain specialists, and other health-care personnel working with this patient group.

The systematic review from 2012 that we seek to build on is widely used, even though the data may be outdated.² This study is necessary to avoid false assumptions regarding the contemporary risk of persistent pain after KA. We are certain that the results from this study will be used by clinicians to guide patients in their decision to undergo KA or not.

References

1. Gademan, M. G. J., Hofstede, S. N., Vliet Vlieland, T. P. M., Nelissen, R. G. H. H. & Marang-van de Mheen, P. J. Indication criteria for total hip or knee arthroplasty in osteoarthritis: a state-of-the-science overview. *BMC Musculoskelet. Disord.* **17**, 463 (2016).

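### Does it matter that the plan does not say how pain-free respondents, who skip questions 4 to 17, enter the NRS, WOMAC and DN4 medians?

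*Combined protocol and SAP*

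**What the plan says.** Methods, Questionnaire, sets the skip: "patients answering 'No' to question 3 skips questions 4-17 concerning pain in the operated knee". The description of question 3 repeats it: "This question is mandatory due to branching purposes, i.e. respondents without pain can skip questions 4-17". The skipped block holds the NRS (question 4), WOMAC pain (5 to 9), interference (10) and the DN4 interview (11 to 17). Few items are compulsory: "Only questions 3, 4, 20, and 21 are mandatory because we wanted to avoid non-respondents". The WOMAC and DN4 items are therefore optional even for patients with pain.

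Methods, Statistical analyses, then plans these summaries:

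- **NRS:** "The raw NRS score, height and weight are continuous variables and will be reported as median (interquartile range [IQR]) number of respondents".
- **WOMAC pain total:** "This results in an overall score of 0-20, which will be reported as median (IQR"), with no n.
- **DN4:** "Both the median (IQR) DN4 interview score and number of patients (percentage of all patients) with possible neuropathic pain will be reported", with no n beside the median.
- **Categorical items**, including the single WOMAC and DN4 items: counts, with percentages that use all patients as the denominator.

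The missing-data paragraph opens with "We do expect some missing data because incomplete questionnaires may be submitted". It rules out imputation in general. The one exception is that a WOMAC or DN4 sum may be completed with the median of the items the respondent did answer.

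**The concern.** A respondent who says the knee no longer hurts has no score on any of the three instruments. Two codings are natural: score the person zero, or leave the person out. The first describes everyone who had the operation; the second describes only those who still have pain. The plan names neither.

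The DN4 sentence makes the difficulty plain. It pairs a median of unstated base with a percentage of all patients, so two adjacent figures could describe different groups. A reader could take a WOMAC or DN4 median as the typical value after knee arthroplasty when it describes only the patients still in pain. Because the items are optional as well, a blank in an item table could seem to have two meanings: pain-free and skipped, or in pain and not answered.

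**Working it through.** **Inputs.** 3172 total knee arthroplasty patients, a 70% response rate and a 16% incidence of NRS above 3 (Methods, Sample characteristics); the Wald interval (Methods, Statistical analyses). The share *f* answering No to question 3 is not in the documents and is treated as an assumption.

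**1. The plan's own figure.** Respondents: 3172 × 0.70 = 2220. Half-width: 1.96 × √(0.16 × 0.84 / 2220) = 0.0153. The interval is 14.5 to 17.5%, width 3.05 points, which agrees with the stated 3 points after rounding. The printed limits (14.6 to 17.6) sit about 0.1 higher, which has no bearing here.

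**2. Primary outcome.** Cases: 0.16 × 2220 = 355. A No at question 3 cannot be an NRS above 3, so skippers are non-cases. With all respondents as denominator the result is 355/2220 = 16.0% for every *f*. By the same reasoning, the percentage with possible neuropathic pain does not depend on how skippers enter the DN4 median.

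**3. Size of the base.** Since 16% have NRS above 3, *f* is at most 1 − 0.16 = 0.84. The base with skippers left out is 2220 × (1 − *f*), so it lies between 355 and 2220.

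**4. Effect on the NRS median.** With skippers left out, the median can exceed 3 only if 0.16/(1 − *f*) is at least 0.5, that is *f* ≥ 0.68. With skippers scored zero, the median is 0 whenever *f* exceeds 0.50. The table assumes that scores among patients with pain are spread evenly over 1 to 3 and over 4 to 8.

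| Assumed *f* | Skippers | Respondents with pain | Median NRS, pain only | Median NRS, skippers as 0 |
|---|---|---|---|---|
| 0.30 | 666 | 1554 | 2 | 2 |
| 0.40 | 888 | 1332 | 3 | 1 |
| 0.50 | 1110 | 1110 | 3 | 0.5 |
| 0.60 | 1332 | 888 | 3 | 0 |

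The choice can therefore move the median or leave it unchanged. No corresponding difference for WOMAC or DN4 can be derived from the documents.

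**5. What the planned output already shows.** Question 3 is a mandatory categorical item, so its No count, which is the number of skippers, is a planned result. Question 4 is mandatory for everyone with pain, and the most natural reading is that an n stands beside the NRS median. At *f* = 0.40 that n would be 1332 if skippers are left out and 2220 if they are scored zero, so the base can be seen. The WOMAC items are reported as counts; adding the counts across an item's five answers shows how many respondents it rests on.

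**6. What the missing-data text implies.** Completing a sum needs at least one answered item. A skipper has none, so the exception yields no score, and the general rule is not to impute. The text is written for incomplete questionnaires rather than a designed skip, so it leans towards leaving skippers out without saying so.

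**The case for a change.** The best case for a change is that the omission is real and costs only a few sentences to close. Scoring no pain as zero is natural too: zero is the no-pain anchor of the NRS and the score for none on WOMAC. The missing-data text does not expressly exclude it. Several questions inside the skipped block were chosen for comparison with the 2004 survey, and the responses feed two later pooled studies, so a written coding rule would be useful. A reader who divided only by those who answered question 4 would get 0.16/0.70 = 23% at *f* = 0.30 and 0.16/0.40 = 40% at *f* = 0.60, instead of 16%.

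Part of this stands. The plan does not name the base of the WOMAC and DN4 medians, gives them no n, and does not expressly plan item-level counts of unanswered questions.

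The rest is weaker. A blank item is not ambiguous in the data, because the mandatory question 3 shows whether it was skipped or unanswered. A separate row for skippers would repeat the question 3 count. The 23 to 40% reading conflicts with the stated denominator of all patients. Which base suits DN4 is a matter of preference.

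Appendix 3 (Survey in English) also prints the question 4 condition against question 1 instead of question 3. Question 1 has no answer No, and the Methods twice name question 3, so this is a clerical slip. The Danish questionnaire is not shown, so nothing can be inferred about the version sent to patients.

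**Conclusion.** No change to the plan is needed. The gap is one of labelling, in two secondary descriptive medians. An analyst must choose a base to compute them, either choice is sound, and stating the base and n beside the result is ordinary table-making. The planned question 3 counts, the NRS n and the item counts let a reader work out most of what is left unsaid.

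The effect on the primary result is nil: 16.0% for any pain-free share, provided all patients means all respondents including those who skip. Inflating the sample size for a 70% response rate supports that reading, though the plan does not define the term. The 1554 to 888 range for the pain-only base rests on an assumed pain-free share of 30 to 60%, and the illustrative NRS medians also rest on an assumed spread of scores.

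### Do the sample-size figures (16%, 70% response, 3172 patients, 14.6-17.6%) contradict each other?

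*Combined protocol and SAP*

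**What the plan says.** Methods, Sample characteristics, sets the size of the survey by precision. The calculation concerns total knee arthroplasty: "The sample size calculation is based on the primary outcome in total KA patients". The inputs are "With an estimated 16% incidence of the primary outcome" "and a 70% response rate", and the result is that "3172 patients are needed to yield a 95% confidence interval of 3 percentage points (14.6-17.6" percent. The paragraph names no interval method. It adds that four months of operations outside the holiday season "should yield approximately this number of identified patients".

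Methods, Statistical analyses, gives the only interval formula in the document, p ± 1.96 √(p(1−p)/n). It is introduced for the final report: "The main outcome will be reported as percentage of all patients with 95% confidence interval", "calculated with assumed binomial distribution".

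**The concern.** A reader who checks the planned precision will reach for the one formula printed, and it does not return the printed limits. The formula is symmetric about p, so at 16% the limits must centre on 16.0%, whereas (14.6 + 17.6)/2 = 16.1%. The width at the planned number of respondents is also slightly above 3.00 points. A reader could conclude that the limits are wrong, or that 3172 is too few.

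This is the plan's only precision statement, and the plan uses it to argue that the survey is large enough. If the number were really too small, the survey would be less precise than promised.

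**Working it through.** **Inputs.** From Sample characteristics: p = 0.16, response rate 0.70, N = 3172, width 3 points, limits 14.6-17.6. From Statistical analyses: z = 1.96 and the symmetric (Wald) formula. Using that formula for planning is an assumption.

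**1. Respondents.** 3172 × 0.70 = 2220.4, so 2220.

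**2. Reporting formula at the planned inputs.** 1.96 × √(0.16 × 0.84/2220) = 0.01525. Limits 14.475-17.525%, which print as 14.5-17.5; width 3.05 points. The printed limits are not reproduced. At p = 0.16, no n from 300 to 8000 rounds to 14.6-17.6 with this formula.

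**3. Number for a width of exactly 3.00 points, same formula.** 4 × 1.96² × 0.16 × 0.84/0.03² = 2294.7, so 2295 respondents; 2295/0.70 = 3278.6, so 3279 patients, 107 (3.4%) above 3172. This gap exists only if the stated 3 points means 3.00. The plan prints a whole number.

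**4. Does another standard binomial interval fit the printed figures?** The Wilson interval has centre (p + z²/2n)/(1 + z²/n) and half-width [z/(1 + z²/n)] √(p(1−p)/n + z²/4n²). Its centre is pulled towards 50%, so it lies above p here, as the printed limits do.

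| Proportion at n = 2220 | Wilson limits (%) | Printed to one decimal | Width (points) |
|---|---|---|---|
| 0.16 exactly (355.2 patients) | 14.53-17.58 | 14.5-17.6 | 3.05 |
| 355/2220 = 15.99% | 14.53-17.57 | 14.5-17.6 | 3.05 |
| 356/2220 = 16.04% | 14.57-17.62 | 14.6-17.6 | 3.05 |

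Sixteen per cent of 2220 is 355.2, which is not a possible count. Rounded up to 356, the Wilson interval gives the printed limits.

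**5. Does the same method give 3172?** At p = 0.16 the smallest n with a Wilson width below 3.05 points, so one that rounds to 3.0, is 2220. Then 2220/0.70 = 3171.4, which rounds up to 3172.

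**6. A second route to the printed limits.** With the reporting formula at n = 2220, an unrounded incidence of about 16.08-16.12% also prints as 14.6-17.6; at 16.1% it gives 14.57-17.63, width 3.06.

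The printed figures are therefore compatible with one another under at least two readings, each of which leaves 3172 as it stands.

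**The case for a change.** The best case for acting is that a precision claim should be reproducible from what is printed, and this one is not. That stands: the printed formula with the printed incidence cannot give 14.6-17.6 at any n in the range scanned. The Wilson route also needs three things the plan does not say: the method, rounding the count up to 356 (355 gives 14.5-17.6), and reporting a width of 3.05 as 3. If that route is right, the survey was planned with one interval method and will be reported with another, without saying so. A line naming the method would cost almost nothing.

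A stronger version says that Wilson at 16% gives 14.6-17.6 only for 2272-2313 respondents, or 3246-3305 patients at 70%, which would leave 3172 short. This does not stand. It holds the incidence at exactly 0.16000, which is not a possible count at 2220, although the plan gives only an estimate to the nearest per cent. The 107-patient shortfall likewise depends on reading 3 points as 3.00.

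The mismatch in method is harmless at this size. At n = 2220 and 16%, the two intervals differ by about 0.06 point at each limit (14.475-17.525 against 14.53-17.58) and have the same width to two decimals.

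**Conclusion.** No change to the plan follows. The arithmetic behind the concern is correct but narrow: the reporting formula at 16% and 2220 respondents gives 14.5-17.5%, 0.1 point from each printed limit, with a width of 3.05 points. It does not show that any printed figure is wrong, because the plan does not say that this formula was used for planning, and 356/2220 with a Wilson interval matches the incidence, response rate, patient number, limits and rounded width together. That this was the authors' method is an inference. The unrounded incidence in the cited register report cannot be checked from the document.

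What is left is a missing detail with no consequence. The patient number is what a fixed four-month window is expected to yield approximately, not a target at which recruitment stops. There is no hypothesis test, stopping rule or decision threshold. The published interval will come from the observed count and the formula already specified. Naming the planning method would tidy the text, but it would change neither whom the survey invites, nor how the outcome is analysed, nor what can be concluded.

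### Filling missing DN4 items with a median, with no minimum number answered, forces a neuropathic-pain class that the answers do not settle, in either direction

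*Combined protocol and SAP*

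**What the plan says.** All references are to the combined protocol and SAP.

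- **Scoring (Methods, Statistical analyses).** "Each of the seven questions in the DN4 interview can be scored 0/1 (no/yes), which results in an overall score of 0-7". The cut-off follows: "A score ≥ 3 constitutes 'possible' neuropathic pain". Besides the median score, the "number of patients (percentage of all patients) with possible neuropathic pain will be reported".
- **Missing items (same section, missing-data paragraph).** "We do expect some missing data because incomplete questionnaires may be submitted". Responses are generally not imputed, but for the two summary scores the authors will "impute values to calculate summary scores of the WOMAC pain domain and DN4 interview as the median of the reported values within the instrument".
- **Which items can be blank (Methods, Questionnaire).** "Only questions 3, 4, 20, and 21 are mandatory because we wanted to avoid non-respondents". The DN4 items are questions 11-17, so any of them may be left blank. A patient who answers No "to question 3 skips questions 4-17 concerning pain in the operated knee"; those patients are routed past the DN4 and are not missing.
- **Item-level reporting (Statistical analyses).** Categorical variables, "including the individual questions of WOMAC pain domain and DN4 interview, will be reported directly", so the single DN4 items are shown without imputation.

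The text gives no minimum number answered, no handling of a tied median, no expected rate of skipped items and no sensitivity analysis for the rule. It does not say whether the median is the patient's own or is taken across respondents.

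**The concern.** The median of a set of 0/1 answers is 0, 1 or, in a tie, 0.5. Filling blanks with it is therefore close to a majority vote: all blanks become Yes, all become No, or each becomes half a Yes. When few items are answered, the vote rests on almost nothing. One Yes and six blanks scores 7, the maximum. One No and six blanks scores 0. Neither patient's answers show on which side of 3 the full score would fall, yet both are classed as if they did.

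At stake is a promised result, the number and percentage with possible neuropathic pain. Two analysts could also code the rule differently and both comply with the plan. The missing minimum affects the WOMAC pain sum too: one answered item rated Severe (3) and four blanks gives 3 + 4 x 3 = 15 out of 20. That score has no cut-off, so the effect there is probably small.

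**Working it through.** The plan states no figure that depends on this rule, so there is none to reproduce. The check enumerates the answer patterns and then works through assumed scenarios.

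**Inputs from the documents.** Seven items scored 0/1; cut-off 3; blanks allowed; blanks filled with the median of the reported values.

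**Step 1: enumeration, median within the patient.** Let y be the number of Yes, n the number of No, and b = 7 - y - n the blanks.

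Score = y + b x median of the answered items.

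There are 27 patterns with at least one answer and one blank. A pattern is unsettled when y < 3 but y + b >= 3. Fourteen are unsettled:

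| Rule's class | Patterns (Yes/No) |
|---|---|
| Possible (5) | 1/0, 1/1, 2/0, 2/1, 2/2 |
| Not possible (9) | 0/1, 0/2, 0/3, 0/4, 1/2, 1/3, 1/4, 2/3, 2/4 |

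The five scores at or above 3 are:

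- 1/0: 1 + 6 x 1 = 7
- 1/1: 1 + 5 x 0.5 = 3.5
- 2/0: 2 + 5 x 1 = 7
- 2/1: 2 + 4 x 1 = 6
- 2/2: 2 + 3 x 0.5 = 3.5

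All five have four or fewer items answered. With ties set to 0, three remain (1/0, 2/0, 2/1). With 5 or 6 items answered, no patient with fewer than three Yes reaches 3, so any error there is downward only (1/4, 2/3, 2/4).

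**Step 2: the other reading.** If the median were taken across respondents and fewer than half say Yes, every blank becomes 0 and none of the five lifts occurs.

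**Step 3: size under assumptions.** The documents give neither a skip rate nor item frequencies. The assumed model is 1,000,000 patients with pain, with a common item probability per patient drawn from a beta distribution (means 0.15, 0.20, 0.25; a + b = 3). This gives true shares at or above 3 of 15.8%, 22.4% and 29.5%. Net error is the false-positive share minus the false-negative share.

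| Assumed behaviour (patients with pain) | False positives | Net error, points |
|---|---|---|
| 5% of items blank at random | 0.01-0.02% | -1.0 to -1.7 |
| 10% of items blank at random | 0.08-0.11% | -1.9 to -3.1 |
| 20% of items blank at random | 0.5-0.6% | -2.9 to -5.0 |
| 10% of patients skip questions 14-17 | about 0.2% | -0.5 to -0.9 |
| 10% of patients mark only Yes | all of the error | +3.1 to +3.7 |

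With 10% random blanks, 0.25-0.40% of patients are lifted to 3 or more with fewer than three Yes, and most of these truly belong there (false positives 0.08-0.11%). On the across-respondent reading with median 0, the same blanks give -2.2 to -3.5 points, and marking only Yes gives no error.

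**Step 4: all respondents.** If 30-60% have pain (assumed), 10% random blanks give -1.93 x 0.3 = -0.6 to -3.14 x 0.6 = -1.9 points. With 10% marking only Yes, it is 3.07 x 0.3 = +0.9 to 3.69 x 0.6 = +2.2 points.

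**The case against.** The strongest reply is that the upward lifts look dramatic but are rare. They need four or fewer of seven answers. Under random blanks they are mostly correct, and the dominant error is downward. A large upward error needs patients who mark Yes and leave No blank. Appendix 3 prints both options for every item, so this is less likely, although the question stems ask about one or more characteristics. Weight and height are mandatory and come after the DN4 items; if mandatory means that the form cannot be submitted without them, simple break-off would not produce such patterns. This stands, and it is why the point is not that the rule inflates the percentage. Skipping a block of items remains possible.

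A second reply is that some of the gaps are small. With no DN4 answer there are no reported values, so the rule yields no score, and 3.5 still classifies against a cut-off of 3. This is true, but 3.5 is not a valid count on a 0-7 scale, and the class of a patient with pain and no DN4 answer is still not stated.

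A third reply concerns the remedy: a 5-of-7 minimum alone would not give an honest range. This also stands. If everyone with at least five answers and fewer than three Yes were called negative, the all-No to all-Yes range with 10% random blanks would run from -2.9 to -0.6 points and from -3.5 to -1.3 points around the truth in two of the three settings, and so would exclude it. The classification must therefore be stricter than the scoring minimum.

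**Conclusion.** The concern holds as a minor point. The enumeration is exact: on the within-patient reading, the rule assigns a class to 14 patterns whose answers do not settle it, 5 upward and 9 downward. The consequence is not known. It rests on assumed skipping behaviour and item frequencies, and its sign changes with them.

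A reader might infer that the plan will overstate neuropathic pain. The documents do not support that: no passage describes patients marking only Yes, and under random or block skipping the net error is downward. Nor is the main result at risk. The primary outcome (NRS above 3) uses a question that is mandatory for patients with pain and is not imputed, and the single DN4 items are reported as answered.

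**What to change.** Add to the missing-data paragraph:

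- The median is taken within the patient.
- The DN4 score is imputed only with at least 5 of 7 items answered, and a tied median is set to 0 (at that minimum, this affects only three Yes and three No). The 5-of-7 threshold is a conventional choice, not one taken from the documents. The WOMAC pain sum is computed only above a pre-specified minimum, for example 4 of 5.
- For the percentage, a patient is possible with three or more observed Yes, not possible only when observed Yes plus blanks is below 3, and otherwise undetermined. The undetermined group includes 1/4, 2/3, 2/4 and patients with pain and no DN4 answer.
- Patients routed past questions 4-17 by No to question 3 are not undetermined.
- The number undetermined is reported, and the percentage is shown on one stated denominator with the undetermined counted as all No and as all Yes. This is then a strict bound on the effect of the blanks.

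The cost is a few sentences and a few lines of R, with no change to the questionnaire. The downside is a wider range: about 4-6% of patients with pain would be undetermined with 5% random blanks, and about 10-13% with 10%. The score and the percentage may also cover slightly different patients (three Yes and four blanks is possible but has no score), so both numbers of patients should be stated.
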